9.3.6 Menstruation

Caregivers will be asked if the female patient is menstruating and details will be recorded at Visit 1; any changes in normal cycles will be captured at Visit 8, Visit 10, and Visit 14 (end of treatment).

Menstruation details will be summarized as appropriate by visit.

9.4 Other Measures

9.4.1 Concomitant Medication

Medications will be coded using the World Health Organization Drug Dictionary WHO-DD Enhanced (v. WhoDrugGlobalB3 - 201903) or later version.

All medication will be considered concomitant.

For summaries and listings of medications the following approach will be used to determine the Anatomical Therapeutic Chemical (ATC) term to be presented:

- If coded to level 4 then the level 4 coded term will be presented.
- If coding is not performed at level 4 but level 3 coding is present then level 3 coded term will be presented.
- If coding is not performed at level 3 but level 2 coding is present then the level 2 coded term will be presented.
- If coding is not performed at level 2 but level 1 coding is present then the level 1 coded term will be presented.

Concomitant medications by ATC term and preferred term will be summarized by absolute counts (n) and percentages (%).

The ATC term, preferred term, reported generic name and reported brand name will be listed.

9.4.2 Procedures and Non-Drug Therapies

Procedures and non-drug therapies will be summarized overall.

9.4.3 Pregnancy Monitoring Form

Any patient who has become pregnant whilst receiving IMP, or within 90 days of last dose of IMP, must be reported to the GW PVD. Where possible the investigator should provide the outcome of the pregnancy and complete the pregnancy monitoring form. Details of pregnancies will be listed.

9.4.4 Patients Impacted by COVID-19

A listing of all patients impacted by COVID-19 related study disruption will be provided. The listing will include patient ID, site and a description of how the patient's participation was altered.

Protocol Deviations related to COVID will be provided in a data listing.

9.5 Changes in the Conduct of the Trial or Planned Analysis

After carefully evaluating the study performance and the potential impact of the COVID-19 pandemic to patients and site personnel the Sponsor made the decision to discontinue the lead-in trial. The significant challenges to conducting studies in this vulnerable group of patients were magnified by the COVID-19 pandemic leading to the conclusion that it was no longer feasible to conduct the studies. All patients enrolled in GWND18064 continued the study as per plan and if agreed, entered the OLE extension. When entering the OLE extension, patients will complete this trial as per protocol and annex. The annex described conditions for patients entering the extension trial if they withdrew from RCT trial due to Covid, due to sponsor administrative decision or delayed entry into GWND19002 due to Covid. All OLE trial Visit 1 data will be summarized for patients enrolling in the OLE under this protocol annex. Their data will be summarized in the same way as that of patients enrolling in the OLE under the GWND19002 protocol. The summary tables will present data from patients enrolling in the OLE under the protocol annex combined with that of patients enrolling in the OLE under the GWND19002 protocol. Their data will also be presented separately.'

As a result the analyses described in this SAP differ from those that were initially intended and presented in the protocol. Initially only comparison towards RCT baseline was planned, in this SAP both comparison with RCT and OLE baseline is planned.

10. References

1. US Federal Register. (1998) International Conference on Harmonization; Guidance on Statistical Principles for Clinical Trials. Department of Health and Human Services: Food and Drug Administration [Docket No. 97D-0174]. Federal Register Volume 63, Number 179, pages 49583-49598. September 16, 1998.
2. ASA. (2016) Ethical Guidelines for Statistical Practice. Prepared by the Committee on Professional Ethics, April 2016. <http://www.amstat.org/about/ethicalguidelines.cfm>
3. RSS. (2014) The Royal Statistical Society: Code of Conduct, 2014. <http://www.rss.org.uk/Images/PDF/join-us/RSS-Code-of-Conduct-2014.pdf>.
4. HealthActCHQ. (2013). The CHQ Scoring and Interpretation Manual. Boston, MA: HealthActCHQ.
5. Maruish, M. (2011). User's manual for the SF-36v2 Health Survey (3rd ed.). Lincoln, RI: QualityMetric Incorporated.

11. Tables, Listings, and Figures

Table, listings and figures shells are provided as a separate document. The final statistical tables will be produced in the format of the shells and will additionally include “double” page numbering in the format “page xx of yy”. Note that programming notes may be added or modified if appropriate after each TLF shell.

The final statistical output will be provided as fully bookmarked pdf file including a table of contents.

All listings, tables, and graphs will have a header showing the sponsor company name and protocol and a footer showing the version of SAS, the file name and path, and the source of the data (eCRF page or listing number).

In general, one listing will be produced per eCRF domain. All listings will be sorted by site, and patient number.

In all listings a blank line will be placed between each patient. Within a data listing, if an item appears line after line (eg, repetition of patient number), then only the first occurrence will be displayed.

In data listings, the information for one patient will be kept on one page if at all possible, rather than splitting a patient’s information across pages.

APPENDIX 1: Abbreviations

Abbreviation	Definition
AE	Adverse event
CRO	Contract research organization
CSR	Clinical study report
D	Day
eCRF	Electronical case report form
ITT	Intent-to –treat analysis set
ECG	Electrocardiogram
EMA	European Medicines aAgency
FDA	Food and Drug Administration
ICH	International Conference on Harmonisation
MedDRA	Medical ictionary for regulatory activities
OLE	Open-Label Extension
PD	Pharmacodynamics
PP	Per-protocol population
PK	Pharmacokinetics
QTc	QT-interval for ECG corrected for heart rate
SAE	Serious adverse event
SAP	Statistical analysis plan
SD	Standard deviation

Abbreviation	Definition
SAF	Safety population
SOC	System organ class
TEAE	Treatment-emergent adverse event
WHO	World Health Organization

APPENDIX 2 Adverse Events of Special Interest – Abuse Liability based on preferred term

Withdrawal	
 Drug withdrawal convulsions Drug withdrawal headache Drug withdrawal maintenance therapy Drug withdrawal syndrome Drug withdrawal syndrome neonatal Drug rehabilitation Rebound effect Steroid withdrawal syndrome Withdrawal arrhythmia Withdrawal syndrome
Drug abuse and dependence	
 Dopamine dysregulation syndrome Drug abuse Drug abuser Drug dependence Drug dependence, antepartum Drug dependence, postpartum Intentional drug misuse Intentional overdose Maternal use of illicit drugs Neonatal complications of substance abuse Polysubstance dependence Substance abuse Substance abuser Accidental overdose Dependence Disturbance in social behaviour Drug administered at inappropriate site Drug detoxification Drug diversion Drug level above therapeutic Drug level increased Drug screen Drug screen positive Drug tolerance Drug tolerance decreased Drug tolerance increased Medication overuse headache Narcotic bowel syndrome Needle track marks Overdose Prescribed overdose Prescription form tampering Substance use Substance-induced mood disorder Substance-induced psychotic disorder Toxicity to various agents

APPENDIX 3 Ranges for Clinically Significant Changes and Other Defined Flagged Values in Vital Signs

The range of values that will be used to identify clinically significant changes in vital signs parameters (See [Section 9.3.1](#)) are presented in [Table 7](#).

Table 7 Ranges for Potentially Clinically Significant Changes in Vital Signs

Vital Sign	Range
Sitting Systolic BP (mmHg)	Change: < -20, > 20
Sitting Diastolic BP (mmHg)	Change: < -10, > 10
Pulse Rate (bpm)	Change: < -10, > 10
Weight (kg)	Percent Change: $\leq -7, \geq 7$

Defined flagged values that will be used to identify low or high vital signs parameters (See [Section 9.3.1](#)) are presented in [Table 8](#).

Table 8 Other Defined Flagged Values for Vital Signs

Vital Sign	Flag
Sitting Systolic BP (mmHg)	< 90, > 140, > 160
Sitting Diastolic BP (mmHg)	< 50, > 90, > 100
Pulse Rate (bpm)	< 60, > 100
Temperature (°C)	> 38.0, < 36.0
Respiratory Rate (breaths/min)	< 12, > 20

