3.3 Study Population

Same study population as the one defined at entry in lead-in trial:

- Female or male patients aged 2–18 years (inclusive), who weight at least 10 kg at entry in lead-in trial.
- At entry in lead-in trial, patients must have a clinical diagnosis of RTT (typical or atypical), defined according to RettSearch Consortium criteria. Patients must have a confirmed pathogenic genetic mutation of the *MECP2* gene.

Patients can be enrolled if they qualify for inclusion criteria and if they do not meet any exclusion criteria for GWND19002 protocol and annex. For complete list of inclusion/exclusion criteria, please consult clinical study protocol and annex.

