7.3 Demographics and Other Baseline Characteristics

The following demographic data will be summarized overall for the safety analysis sets:

- Age (years);
- Age group (2-5 years, 6-12 years and 13-19 years);
- Sex;
- Race;
- Ethnicity
- Country;
- Region (United States, Rest of the World);

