9.2 Clinical Laboratory Evaluation

9.2.1 Hematology and Biochemistry

Hematology and biochemistry safety parameters are measured at Visit 1, Visit 4, Visit 5, Visit 6, Visit 8, Visit 9, Visit 10, Visit 12 and Visit 14 (end of treatment).

Summaries will be presented for each laboratory parameter at each visit. Change from baseline (RCT and OLE baseline) and percent change from baseline to each post-baseline visit will also be presented.

If values for any of the parameters are below or above the limit of quantification of the assay (BLQ or ALQ), then they will be included in the summary tables at the BLQ or ALQ thresholds.

Where laboratory samples are repeated, the baseline value is defined as the final recorded value prior to the first dose of IMP during the lead-in trial or prior to Visit 1 in OLE trial.

Shift tables for hematology and biochemistry parameters will be produced, based upon normal ranges and GW toxicity limits (See [Appendix 3](#)), to determine the categorical shifts from each baseline (RCT and OLE) to each post-baseline visit. Values will be categorized as ‘Normal’, ‘Low’ or ‘High’ based on normal ranges and ‘Toxically Low’, ‘Toxically Normal’ or ‘Toxically High’ based on GW toxicity limits.

For eGFR, results will be assigned to the following grades:

- Normal: >60 ml/min/1.73 m²
- Grade 1: 60 ml/min/1.73 m²
- Grade 2: ≥ 30 and <60 ml/min/1.73 m²
- Grade 3: ≥ 15 and <30 ml/min/1.73 m²
- Grade 4: <15 ml/min/1.73 m²

A separate shift table will be produced for eGFR based upon the above grades to determine the categorical shifts from baseline to each post-baseline visit.

An additional table will be produced, summarizing the number of patients meeting the following criteria:

- Alanine aminotransferase (ALT) $> 1 \times \text{ULN}$ at baseline
- Aspartate aminotransferase (AST) $> 1 \times \text{ULN}$ at baseline
- AT $> 1 \times \text{ULN}$ at baseline
- Treatment-emergent ALT $> 3 \times \text{ULN}$, $> 5 \times \text{ULN}$ and $> 8 \times \text{ULN}$
- Treatment-emergent AST $> 3 \times \text{ULN}$, $> 5 \times \text{ULN}$ and $> 8 \times \text{ULN}$
- Treatment-emergent AT $> 3 \times \text{ULN}$, $> 5 \times \text{ULN}$ and $> 8 \times \text{ULN}$
- Treatment-emergent AT $> 3 \times \text{ULN}$ and either bilirubin $> 2 \times \text{ULN}$ or INR > 1.5

where AT is AST or ALT, and treatment emergent is defined as criteria not met at baseline, but

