9.3 Vital Signs, Other Physical Findings and Other Safety Data

9.3.1 Vital Signs

Vital signs (systolic blood pressure, diastolic blood pressure and pulse rate) are measured at Visit 1, Visit 4, Visit 5, Visit 6, Visit 7, Visit 8, Visit 9, Visit 10, Visit 12, Visit 14 (end of treatment) and Visit 15 (end of taper).

Summaries will be presented for each vital sign parameter at each visit. Change from baseline (RCT and OLE baseline) to each post-baseline visit will also be presented.

A separate table will be produced, by visit, presenting the incidence of patients with vital signs indicative of a medical condition at Visit 1 and indicative of an AE after Visit 1.

Based on the criteria presented in [Appendix 3](#), potentially clinically significant changes from baseline (RCT and OLE baseline) in vital signs measurements and other defined flagged values will be identified at each visit. The number of patients with a potentially clinically significant change from baseline will be summarized by parameter, and visit. The number of patients with at least one post-baseline flagged vital sign parameter value will be summarized by parameter, and flagged criteria.

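### The vital-sign flag counts use one set of limits for ages 2 to 19 and include patients already flagged at baseline, so they cannot be read as treatment-emergent abnormality.

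*SAP*

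**What the plan says.** SAP Appendix 3, Table 8 lists "Defined flagged values that will be used to identify low or high vital signs parameters". For the three signs this trial measures, the limits are systolic pressure below 90, above 140 and above 160 mmHg; diastolic pressure below 50, above 90 and above 100 mmHg; and pulse below 60 and above 100 bpm. They apply to every patient.

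SAP section 9.3.1 sets the counting rule: "The number of patients with at least one post-baseline flagged vital sign parameter value will be summarized by parameter, and flagged criteria". It sets no condition on baseline status and no age split.

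Three other parts of the SAP bear on this:

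- Section 9.2.1, for the ALT and AST criteria: "treatment emergent is defined as criteria not met at baseline".
- Section 7.3, for demographics: "Age group (2-5 years, 6-12 years and 13-19 years"). These groups are not carried into section 9.3.1. Section 3.3 gives the age range at lead-in entry as 2 to 18.
- Section 6.1.2 defines two baselines, RCT and OLE. Section 9.3.1 does not say which one the flag count uses.

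**The concern.** Vital signs are part of the primary safety endpoint (Protocol section 4.1.1; SAP section 2.2.2). A reader of the flag table will want to know how many patients developed a low or high value on treatment. The rule does not answer that. A patient above a limit before any drug, and unchanged afterwards, is counted in the same way as one who crossed it during treatment.

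Every patient receives GWP42003-P in the extension, so no concurrent untreated group shows the background flag rate. Baseline status is then the main way to separate old from new, and this table does not use it. Applying one limit across ages 2 to 19, without showing age, also means that a count may reflect the age mix rather than any change.

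**Working it through.** The plan states no expected flag rate, so there is no figure to reproduce. The check has two parts: how the rules differ, and how much that could matter.

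**Rules side by side**

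| Output | Baseline condition | Split |
|---|---|---|
| Table 8 flags (9.3.1) | none | parameter and criterion |
| Table 7 changes (9.3.1) | change from each baseline | parameter and visit |
| ALT/AST criteria (9.2.1) | criterion not met at baseline | overall and by co-medication |

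Only the Table 8 count admits a pre-existing abnormality.

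**Inputs for the illustration**

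- From the SAP: the pulse limit of 100 bpm, and up to 10 vital-sign visits after Visit 1 (Visits 4 to 10, 12, 14 and 15).
- Assumed: group mean pulse 80 to 110 bpm; between-patient SD 10 and within-patient SD 8; no drug effect; 3 or 10 visits. Three visits are included because the SAP Overview says the extension stopped early and some assessments will not be done.

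**Accumulation over visits.** If visits were independent with flag chance p at each, the chance of at least one flag in k visits is 1 − (1 − p)^k. For p = 5%, 10% and 20% this is 14%, 27% and 49% over 3 visits, and 40%, 65% and 89% over 10.

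**Allowing for stable differences between patients.** Let a patient's own mean be μ, with μ ~ N(m, 10²).

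- Single-visit chance: p(μ) = 1 − Φ((100 − μ)/8).
- Any flag in k visits: A = E[1 − (1 − p(μ))^k].
- Any flag in k visits and also flagged at baseline: B = E[p(μ){1 − (1 − p(μ))^k}].
- Share of flagged patients already flagged at baseline: B/A. Newly flagged: A − B.

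As an example at m = 90, the total SD is √(10² + 8²) = 12.8, so the single-visit chance is 1 − Φ(10/12.8) = 0.217. Ten independent visits would give 1 − 0.783^10 = 0.91. Averaging over μ gives 0.58, because the same patients tend to be flagged repeatedly.

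| Group mean (bpm) | Any flag, 3 visits | Any flag, 10 visits | Share of 10-visit flags present at baseline | Newly flagged, 10 visits |
|---|---|---|---|---|
| 80 | 13% | 24% | 20% | 19% |
| 90 | 39% | 58% | 35% | 38% |
| 100 | 72% | 87% | 57% | 38% |
| 110 | 93% | 98% | 80% | 20% |

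With a between-patient SD of 8 instead of 10, a mean of 80 gives 9% over 3 visits and 20% over 10. A mean of 90 gives 37% and 60%, and a mean of 110 gives 95.5% and 99%.

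Excluding patients flagged at baseline cuts the 10-visit count from 87% to 38% at a mean of 100, and from 98% to 20% at 110. It does not bring the count near zero, so display by age is needed as well.

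**Who is flagged.** Let f be the share of the sample aged 2 to 5, with flag rates qy in that group and qo in older patients. The young share of flagged patients is f·qy / (f·qy + (1 − f)·qo). With assumed rates of 90% and 30%, it is 0.09/(0.09 + 0.27) = 25% at f = 10% and 0.36/(0.36 + 0.18) = 67% at f = 40%. For the youngest group to be the majority, qy/qo must exceed (1 − f)/f, which is 9.0 at f = 10% and 1.5 at f = 40%.

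**The case against.** The flag table does not stand alone. Section 9.3.1 also plans summaries at every visit, change from both baselines, a table separating conditions seen at Visit 1 from later adverse events, and the Table 7 changes: "The number of patients with a potentially clinically significant change from baseline will be summarized by parameter, and visit". Table 7 is a change-from-baseline rule, so a pre-existing value cannot count there by itself. Table 8 claims only to identify low or high values and does not call them treatment-emergent. The trial is single-arm and descriptive, so no version of this table could establish a drug effect. Ten visits is a maximum. The SAP's own age-dependent limit, for lymphocytes, splits only at 18 and is a thin precedent. The table shells are a separate document and might contain a baseline row or an age split.

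Most of this stands, and it limits the severity. It rules out any claim that the vital-sign analysis as a whole would hide a drug effect. It does not repair this count: section 9.3.1 states the rule in full, and unseen shells do not override it. A reader given a count of patients flagged after baseline is likely to take it as new abnormality unless told otherwise.

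**Conclusion.** The point holds for Table 8 only. The counts cannot be read as treatment-emergent abnormality, because they include patients already flagged at baseline and pool ages 2 to 19 under one set of limits. How much this matters depends on pulse means, SDs and numbers of visits that the documents do not give. Under the assumptions above, the share of patients flagged for pulse above 100 with no drug effect runs from roughly a tenth to a quarter at a mean of 80 to nearly everyone at 110.

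A reader might infer that the table will mostly flag normal young children. The documents do not support that. They give neither the age mix nor paediatric norms, and the calculation puts ages 2 to 5 anywhere from 25% to 67% of flagged patients. Rows are also reported separately. If younger children have a faster pulse and lower pressure (an assumption), three of the eight criteria would over-flag them: pulse above 100, systolic below 90 and diastolic below 50. The other five would not, and the high-pressure rows would tend to miss them.

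The change is worth making before the SAP is final, but severity is modest.

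**What to change.** 1. In section 9.3.1, for each Table 8 criterion, keep the present count. Beside it, add the number of patients who meet the criterion after baseline but did not meet it at RCT baseline, as section 9.2.1 does for ALT and AST.
2. Add a second count against OLE baseline. Section 6.1.2 takes that baseline from Visit 1, but the schedule of assessments requires Visit 1 vital signs only when Visit 1 and RCT Visit 9 fall on different days, and same-day entry is recommended. State that the RCT Visit 9 value is used for same-day entrants with no separate Visit 1 value. For patients given GWP42003-P in the lead-in trial this is an on-treatment value, so the RCT-baseline count should come first.
3. Show the Table 8 counts by the three age groups in section 7.3. The sponsor may also specify age-appropriate limits before database lock, with a cited source.

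The cost is a short edit to section 9.3.1 and a few extra table rows, with no new data. The downside is small cells within age groups, more so once the columns for lead-in treatment and protocol or annex enrolment are applied. Age-appropriate limits, if chosen, would also need a lookup table.

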APPENDIX 1 Defined Flagged Values in ECG Parameters

Defined flagged values that will be used to identify low or high ECG parameters (See [Section 9.3.2](#)) are presented in [Table 9](#).

Table 9 Defined Flagged Values for ECG Parameters

ECG Parameter	Flag
QTc (ms)	> 450, > 480, > 500

APPENDIX 2 Toxicity Criteria for Laboratory Parameters

The toxicity criteria that will be used to identify abnormal laboratory parameters are presented in [Table 10](#) and [Table 11](#).

Table 10 Toxicity Criteria for Biochemistry Parameters

Parameter	Toxicity Decrease	Toxicity Increase
Chloride	$\leq 0.96 \times LL$	$\geq 1.04 \times UL$
Calcium	$\leq 0.89 \times LL$	$\geq 1.16 \times UL$
Sodium	$\leq 0.96 \times LL$	$\geq 1.04 \times UL$
Potassium	$\leq 0.90 \times LL$	$\geq 1.10 \times UL$
Glucose (mmol/L)	≤ 3.2	≥ 16
Phosphate	$\leq 0.79 \times LL$	
Cholesterol	$\leq 0.85 \times LL$	$\geq 1.6 \times UL$
AST		$\geq 3 \times UL$
ALT		$\geq 3 \times UL$
Lactate Dehydrogenase		$\geq 2.6 \times UL$
Alkaline phosphatase		$\geq 2 \times UL$
Gamma GT		$\geq 2.6 \times UL$
Bilirubin		$> 2 \times UL$
Albumin	$\leq 0.84 \times LL$	
Total protein	$\leq 0.84 \times LL$	$\geq 1.16 \times UL$
Urea		$\geq 2.6 \times UL$
Blood urea nitrogen		$\geq 2.6 \times UL$
Creatinine		$\geq 2.6 \times UL$
Uric acid		$\geq 1.16 \times UL$

UL = upper limit of reference range LL = lower limit of reference range

Table 11 Toxicity Criteria for Hematology Parameters

Parameter	Toxicity Decrease	Toxicity Increase
Hemoglobin (g/dL)	≤ 9.4	
Hematocrit (%)	≤ 28	
Red cell count	$\leq 0.84 \times LL$	
Mean corpuscular volume	$\leq 0.84 \times LL$	$\geq 1.11 \times UL$
Mean corpuscular hemoglobin	$\leq 0.84 \times LL$	
Mean corpuscular hemoglobin concentration	$\leq 0.84 \times LL$	
Platelets ($\times 10^9/L$)	≤ 74	
Prothrombin time		$> 1.5 \times UL$
Prothrombin international normalized ratio		> 1.5
Total white blood cell count ($\times 10^9/L$)	≤ 2.9	≥ 21
Total neutrophil count ($\times 10^9/L$)	≤ 1.36	≥ 14.7
Segmented neutrophil count ($\times 10^9/L$)	≤ 0.75	≥ 12.3
Eosinophils ($\times 10^9/L$)		≥ 1.5
Basophils ($\times 10^9/L$)		≥ 0.31

Parameter	Toxicity Decrease	Toxicity Increase
Monocytes (x10 ⁹ /L)		≥2.1
Lymphocytes (x10 ⁹ /L) for patients <18 years (auto hematology)	≤1.0	
Lymphocytes (x10 ⁹ /L) for patients <18 years (manual hematology)	≤0.2	
Lymphocytes (x10 ⁹ /L) for patients ≥18 years	≤0.2	

UL = upper limit of reference range LL = lower limit of reference range

